9.5.2.2 Description of Procedures/Assessments Schedule

Please refer to the Schedule of Assessments ([Table 2](#)) for details, giving particular attention to all footnotes.

9.5.2.3 Total Volume of Blood Sampling

[Table 3](#) presents the number of blood samples and the total volume of blood that will be collected throughout the study. Additional samples may be taken at the discretion of the investigator if the results of any tests fall outside reference ranges or clinical symptoms necessitate testing to ensure subject safety.

Table 3 Summary of Blood Sample Volumes

	Sample Volume per Collection (mL)	Number of Collection Time Points	Total Volume Collected (mL)
Clinical laboratory tests	12	Screening: 1 Visits 2, 3, 4, 6, 8; 11/EOT, EOS	12×8=96
T4, TSH, Cortisol, Testosterone, estradiol, Serum OC and PICP, Hydroxy-proline; Fasting prolactin levels	10	Screening: 1 Visits 8; 11/EOT/Early discontinuation	10×3=30
Prolactin, FPG, Insulin, and HbA _{1c} sampling	4	Screening: 1 Visits 2, 6, 8; 11/EOT/Early discontinuation	4×5=20
PK/PD blood sampling	4	Visits 6, 8, and 11/EOT/Early discontinuation (2 samples each); Visit 9 (1 sample only)	7×4=28
Total			174

EOS = End of Study; EOT = End of Treatment; FPG = fasting plasma glucose; HbA_{1c} = hemoglobin A_{1c}; OC = osteocalcin; PD = pharmacodynamic; PICP = carboxyterminal propeptide of type I procollagen; PK = pharmacokinetics; T4 = thyroxine; TSH = thyroid stimulating hormone.

9.5.3 Appropriateness of Measurements

All clinical assessments are standard measurements commonly used in studies of obesity.

The safety assessments to be performed in this study, including hematology analyses, blood chemistry tests, urinalysis, and assessment of AEs, are standard evaluations to ensure subject safety.

9.5.4 Reporting of Serious Adverse Events, Pregnancy, and Events Associated with Special Situations

9.5.4.1 Reporting of Serious Adverse Events

All SAEs, regardless of their relationship to study treatment, must be reported on a completed SAE form by email or fax as soon as possible but no later than 1 business day from the date the investigator becomes aware of the event.

SAEs, regardless of causality assessment, must be collected through the through the last visit and for 28 days after the subject's last dose. All SAEs must be followed to resolution or, if resolution is unlikely, to stabilization. Any SAE judged by the investigator to be related to the study treatment or any protocol-required procedure should be reported to the sponsor regardless of the length of time that has passed since study completion.

The detailed contact information for reporting of SAEs is provided in the Investigator Study File.

For urgent safety issues, please ensure all appropriate medical care is administered to the subject and contact the appropriate study team member listed in the Investigator Study File.

It is very important that the SAE report form be filled out as completely as possible at the time of the initial report. This includes the investigator's assessment of causality.

Any follow-up information received on SAEs should be forwarded within 1 business day of its receipt. If the follow-up information changes the investigator's assessment of causality, this should also be noted on the follow-up SAE form.

Preliminary SAE reports should be followed as soon as possible by detailed descriptions including copies of hospital case reports, autopsy reports, and other documents requested by the sponsor.

The investigator must notify his/her IRB/IEC of the occurrence of the SAE, in writing, if required by their institution. A copy of this communication must be forwarded to the sponsor to be filed in the sponsor's Trial Master File.

9.5.4.2 Reporting of Pregnancy and Exposure to Study Drug through Breastfeeding

Any pregnancy in which the estimated date of conception is either before the last visit or within 28 days of last study treatment or any exposure to study drug through breastfeeding during study treatment or within 28 days of last study treatment must be reported.

If an adverse outcome of a pregnancy is suspected to be related to study drug exposure, this should be reported regardless of the length of time that has passed since the exposure to study treatment.

A congenital anomaly, death during perinatal period, an induced abortion, or a spontaneous abortion are considered to be an SAE and should be reported in the same time frame and in the same format as all other SAEs (see [Section 9.5.4.1](#)).

Pregnancies or exposure to study drug through breastfeeding must be reported by fax or email as soon as possible but no later than 1 business day from the date the investigator becomes aware of the pregnancy. The contact information for the reporting of pregnancies and exposure to study drug through breastfeeding is provided in the Investigator Study File. The Pregnancy Report Form must be used for reporting. All pregnancies must be followed to outcome. The outcome of the pregnancy must be reported as soon as possible but no later than 1 business day from the date the investigator becomes aware of the outcome.

A subject who becomes pregnant must be withdrawn from the study.

9.5.4.3 Reporting of Events Association with Special Situations

9.5.4.3.1 REPORTING OF ADVERSE EVENTS ASSOCIATED WITH STUDY DRUG OVERDOSE, MISUSE, ABUSE, OR MEDICATION ERROR

Adverse events associated with study drug overdose, misuse, abuse, and medication error refer to AEs associated with uses of the study drug outside of that specified by the protocol. Overdose, misuse, abuse, and medication error are defined as follows:

Overdose	Accidental or intentional use of the study drug in an amount higher than the protocol-defined dose
Misuse	Intentional and inappropriate use of study drug not in accordance with the protocol or authorized dose, route of administration, or indication(s) or use of prescription-only study drug without a prescription
Abuse	Sporadic or persistent intentional excessive use of study drug accompanied by harmful physical or psychological effects
Medication error	Any unintentional event that causes or leads to inappropriate study drug use or subject harm while the study drug is in the control of the healthcare professional, subject, or consumer. Such events may be related to professional practice, healthcare products, occupational exposure, procedures, or systems, including prescribing, order communication, product labeling, packaging, nomenclature, compounding, dispensing, distribution, administration, education, monitoring, or use.

All AEs associated with overdose, misuse, abuse, or medication error should be captured on the Adverse Event CRF and also reported using the procedures detailed in [Section 9.5.4.1](#) even if the AEs do not meet serious criteria. Abuse is always to be captured as an AE. If the

AE associated with an overdose, misuse, abuse, or medication error does not meet serious criteria, it must still be reported using the SAE form and in an expedited manner but should be noted as nonserious on the SAE form and the Adverse Event CRF.

9.5.4.3.2 REPORTING OF STUDY-SPECIFIC EVENTS

Study-specific events (listed below) should always be considered as serious important medical events and be entered on the Adverse Event CRF and reported using the procedures detailed in Reporting of Serious Adverse Events ([Section 9.5.4.1](#)), even if the study-specific event does not meet other serious criteria.

- Serotonin syndrome Must have at least 1 of the following: spontaneous clonus; inducible clonus plus agitation or diaphoresis; Ocular clonus plus agitation or diaphoresis; Tremor plus hyperreflexia; Hypertonia plus temperature above 38°C plus ocular clonus or inducible clonus
- Psychosis
- Suicidal behavior
- Priapism
- New onset of valvular heart disease
- New onset pulmonary hypertension
- Malignant neoplasms, with the exception of basal cell and squamous cell carcinomas of the skin
- Fibroadenomas of the breast or ductal carcinoma in situ

The following additional study specific AE of interest should be reported using the procedures detailed in Reporting of SAEs ([Section 9.5.4.1](#)), even if the study-specific event does not meet serious criteria. If the event meets seriousness criteria, it should be reported as an SAE as above. However, if the event listed below does not meet serious criteria, it should be noted as nonserious on the Adverse Event CRF:

- Suicidal ideation
- Euphoria

9.5.4.4 Expedited Reporting

The sponsor must inform investigators and regulatory authorities of reportable events, in compliance with applicable regulatory requirements, on an expedited basis (ie, within specific time frames). For this reason, it is imperative that sites provide complete SAE information in the manner described above.

9.5.4.5 Breaking the Blind

In the case of a medical emergency where the appropriate treatment of the subject requires knowledge of the study treatment given, the investigator may break the randomization code

for an individual subject. In all such cases, the AE necessitating the emergency blind break will be handled as an SAE in accordance with the procedures indicated above. Any broken code will be clearly justified and documented. The medical monitor must be notified immediately of the blind break.

9.5.4.6 Regulatory Reporting of Adverse Events

Adverse events will be reported by the sponsor or a third party acting on behalf of the sponsor to regulatory authorities in compliance with local and regional law and established guidance. The format of these reports will be dictated by the local and regional requirements.

9.5.5 Completion/Discontinuation of Subjects

The investigator may withdraw the subject from the study at any time for safety or administrative reasons. A subject may elect to discontinue the study at any time for any reason. All subjects will continue in the study until the 52-week evaluation is completed. Subjects who discontinue treatment prematurely will be followed up until study completion. All subjects who discontinue the study are to complete the study's early discontinuation procedures indicated in the Schedule of Procedures/Assessments ([Table 2](#)).

The investigator will promptly explain to the subject involved that the study will be discontinued for that subject and provide appropriate medical treatment and other necessary measures for the subject. A subject who has ceased to return for visits will be followed up by mail, phone, or other means to gather information such as the reason for failure to return, the status of treatment compliance, the presence or absence of AEs, and clinical courses of signs and symptoms.

Subjects who discontinue early from the study will be discontinued for 1 of these primary reasons: AE(s), lost to follow-up, subject choice, withdrawal of consent, pregnancy, study terminated by sponsor, or other. In addition to the primary reason, the subject may indicate 1 or more of secondary reasons for discontinuation. Study disposition information will be collected on the Subject Disposition CRF.

Detailed retention strategies will be developed and included in study manual. These include a highly trained and competent staff, easy access to the clinic, reminder and follow-up calls, interactive group sessions with games and hands-on nutrition and physical activity demonstrations, random raffle drawings, social events, birthday and holiday cards, and newsletters. In addition, home visits for assessments of families will be an option, as needed, to maximize data collection. This detailed retention plan will help prevent missing data.

A subject removed from the study for any reason may not be replaced.

9.5.6 Abuse or Diversion of Study Drug

During the study, the investigator will report any concern about abuse or diversion of study drugs by completing the Abuse or Diversion of Study Drug CRF. The DEA Registrant has

the responsibility to comply with local, state, and Federal laws to notify the Field Division Office of the DEA of any theft or significant loss of any controlled substances upon discovery of such theft or loss.

9.5.7 Confirmation of Medical Care by Another Physician

The investigator will instruct subjects to inform site personnel when they are planning to receive medical care by another physician. At each visit, the investigator will ask the subject whether he or she has received medical care by another physician since the last visit or is planning to do so in the future. When the subject is going to receive medical care by another physician, the investigator, with the consent of the subject, will inform the other physician that the subject is participating in the clinical study.

9.6 Data Quality Assurance

This study will be organized, performed, and reported in compliance with the protocol, SOPs, working practice documents, and applicable regulations and guidelines. Site audits will be made periodically by the sponsor's or the CRO's qualified compliance auditing team, which is an independent function from the study team responsible for conduct of the study.

9.6.1 Data Collection

Data required by the protocol will be collected on the CRFs and entered into a validated data management system that is compliant with all regulatory requirements. As defined by ICH guidelines, the CRF is a printed, optical, or electronic document designed to record all of the protocol-required information to be reported to the sponsor on each study subject.

Data collection on the CRF must follow the instructions described in the CRF Completion Guidelines. The investigator has ultimate responsibility for the collection and reporting of all clinical data entered on the CRF. The investigator or designee as identified on Form FDA 1572 must sign the completed CRF to attest to its accuracy, authenticity, and completeness.

Completed, original CRFs are the sole property of Eisai and should not be made available in any form to third parties without written permission from Eisai, except for authorized representatives of Eisai or appropriate regulatory authorities.

9.6.2 Clinical Data Management

All software applications used in the collection of data will be properly validated following standard computer system validation that is compliant with all regulatory requirements. All data, both CRF and external data (eg, laboratory data), will be entered into a clinical system.

9.7 Statistical Methods

All statistical analyses will be performed by the sponsor or designee after the study is completed and the database is locked and released for unblinding. Statistical analyses will be performed using WinNonlin and SAS software or other validated statistical software as required. Details of the statistical analyses will be included in a separate statistical analysis plan (SAP).

9.7.1 Statistical and Analytical Plans

The statistical analyses of study data are described in this section. Further details of the analytical plan will be provided in the SAP, which will be finalized before database lock and treatment unblinding.

9.7.1.1 Study Endpoints

9.7.1.1.1 PRIMARY EFFICACY ENDPOINT

- Change in BMI from Baseline to Week 52

9.7.1.1.2 SECONDARY EFFICACY ENDPOINTS

KEY SECONDARY ENDPOINT

- Proportion (%) of subjects achieving at least a 5% BMI reduction at Week 52

OTHER SECONDARY ENDPOINT

- Proportion (%) of subjects achieving at least a 5% BMI reduction at Week 12
- Proportion (%) of subjects achieving at least a 10% BMI reduction at Week 52
- Percentage change in BMI from Baseline to Week 52
- Change and percentage change in BMI from Baseline to Week 52 and proportion (%) of subjects achieving at least a 5% or 10% BMI reduction at Week 52 by the outcome of achieving at least a 5% BMI reduction at Week 12
- Change in waist circumference from Baseline to Week 52
- Change in HbA_{1c} from Baseline to Week 52
- Change in fasting glucose, fasting insulin, and HOMA-IR from Baseline to Week 52
- Change in BP (systolic and diastolic) and heart rate from Baseline to Week 52

- Change in fasting lipid profile (total cholesterol, LDL cholesterol, HDL cholesterol, triglycerides) from Baseline to Week 52
- Proportion (%) of subjects with prehypertension or primary hypertension at Week 52
- Proportion (%) of subjects with dyslipidemia at Week 52

9.7.1.2 Definitions of Analysis Sets

- The Safety Analysis Set is the group of subjects who received at least 1 dose of study drug and had at least 1 postdose safety assessment.
- The Full Analysis Set (FAS) is the group of all randomized subjects regardless of adherence to study drug.
- Per-Protocol Analysis Set (PP) is the group of all randomized subjects who are 80% or greater compliant with study medication, completed the study, have no major protocol deviations, have no violations of inclusion or exclusion criteria, and have BMI data at Baseline and Week 52. The determination of subjects to be excluded from this population based on the above criteria and list of major protocol violations will be included in the SAP and finalized before data base lock.
- The PD Analysis Set is the group of subjects who had sufficient PD data to derive at least 1 PD parameter.
- The PK Analysis Set is the group of all randomized subjects from whom at least 1 valid lorcasein plasma concentration was obtained with associated documented dosing history.
- The population PK/PD set is the group of randomized subjects with PK information and who have at least 1 adequately documented measurement of BMI.

9.7.1.3 Subject Disposition

The number of subjects screened and the number (percentage) of subjects who failed screening and the reasons for screen failure will be summarized, based on data reported on the CRF.

For study completion, the number (percentage) of treated subjects who completed study treatment and who discontinued from study treatment will be summarized according to the primary reason for discontinuation and also according to secondary reason(s) for discontinuation, based on data reported on the CRF. The number (percentage) will be presented by treatment. The reasons for discontinuation from study treatment will be documented in the CRF and source documentation.

9.7.1.4 Demographic and Other Baseline Characteristics

Demographic and other baseline characteristics for the FAS and Safety Analysis Sets will be summarized for each treatment group using descriptive statistics or frequency count. Continuous demographic and baseline variables include age, height, BMI, waist circumference, and weight; categorical variables include sex and race.

9.7.1.5 Prior and Concomitant Therapy

All investigator terms for medications recorded in the CRF will be coded to an 11-digit character code using the World Health Organization Drug Dictionary. The number (percentage) of subjects who took prior and concomitant medications will be summarized for the Safety Analysis Set by treatment group, Anatomical Therapeutic Chemical class, and World Health Organization Drug Dictionary preferred term (PT). Prior medications will be defined as medications that stopped before the first dose of study drug. Concomitant medications will be defined as medications that started on or after the date of the dosing of study drug and continued up to 30 days afterward.

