 7. Use of other products intended for weight loss including prescription drugs, over-the-counter (OTC) drugs, and herbal preparations within 1 month before Screening
 8. Use of any of the following medications:
 - a) Serotonergic drugs within 7 days (or 5 half-lives, whichever is longer) or monoamine oxidase inhibitors (MAOIs) within 30 days before Randomization, including:
 - selective serotonin reuptake inhibitors (SSRIs)
 - serotonin norepinephrine reuptake inhibitors (SNRIs)
 - tricyclic antidepressants (TCAs)

- bupropion
 - triptans
 - St. John's Wort
 - tryptophan
 - linezolid
 - dextromethorphan in any form (eg, OTC cold medicines)
 - lithium
 - tramadol
 - antipsychotics or other dopamine antagonists
- b) Others
- antiseizure medications including valproic acid, zonisamide, topiramate and lamotrigine
 - oral steroids (topical and inhaled steroids are acceptable)
 - stimulant medications (Ritalin, Concerta, Biphedamine and Dexedrine)
 - benzodiazepines
9. Use of drugs known to increase the risk for cardiac valvulopathy within 6 months before Screening, including but not limited to pergolide, ergotamine, methysergide, and cabergoline
 10. History or evidence of clinically significant disease (eg, malignancy; cardiac, respiratory, gastrointestinal, renal, or psychiatric disease) other than prediabetes (impaired fasting glucose or impaired glucose tolerance), Type 2 diabetes treated with oral anti-diabetic agents (excluding sulfonylurea) or non-insulin injectable antidiabetic agents, obstructive sleep apnea, dyslipidemia, and nonalcoholic fatty liver disease
 11. Use of Belviq XR within 6 months before Screening or hypersensitivity to Belviq XR or any of the excipients
 12. Significant change in diet or level of physical activity within 1 month before dosing or change in weight of more than 5 kg within 3 months before Screening
 13. Any use of a of very-low-calorie (<1000 calories/day) weight loss diet within 6 months before Screening
 14. History of alcohol or drug dependence or abuse
 15. Recreational drug use within 2 years before Screening
 16. Known to be human immunodeficiency virus positive
 17. Active viral hepatitis (B or C) as demonstrated by positive serology
 18. Malignancy within 5 years before Screening
 19. Unable to attend scheduled visits (eg, lack of transportation) or lack of a caregiver or guardian to supervise study participation

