20. Special needs subjects who are unable to comprehend study-related instructions (eg, mild to profound mental retardation [IQ <70], moderate to severe cognitive developmental delay, pervasive development disorders, autism)
21. Ongoing epilepsy or other seizure disorder, or use of medications for a seizure disorder within 6 months of screening or any time between screening and randomization
22. Subjects with a BP in the 95th percentile or greater for age, sex, and height on 2 separate readings recorded on 2 separate days. Those subjects who had uncontrolled hypertension at Screening can be rescreened more than 1 month after initiation or adjustment of antihypertensive therapy 1 time.
23. Currently enrolled in another clinical study or has used any investigational drug or device within 30 days before providing informed consent
24. Planned bariatric surgery during the study
25. Not suitable to participate in the study in the opinion of the investigator, including consideration of any existing physical, medical, or mental condition that prevents compliance with the protocol
26. Female subjects who are breastfeeding or pregnant at Screening or Baseline (as documented by a positive β -human chorionic gonadotropin test). A separate Baseline assessment is required if a negative screening pregnancy test was obtained more than 72 hours before the first dose of study drug.
27. Female subjects of childbearing potential who:
 - a. Had unprotected sexual intercourse within 30 days before study entry and who do not agree to use a highly effective method of contraception (eg, total abstinence, an intrauterine device, a double-barrier method [such as condom plus diaphragm with spermicide], a contraceptive implant, an oral contraceptive, or have a vasectomized partner with confirmed azoospermia) throughout the entire study period and for 28 days after study drug discontinuation
 - b. Are currently abstinent, and do not agree to use a double-barrier method (as described above) or refrain from sexual activity during the study period and for 28 days after study drug discontinuation
 - c. Are using hormonal contraceptives but are not on a stable dose of the same hormonal contraceptive product for at least 4 weeks before dosing and who do not agree to use the same contraceptive during the study and for 28 days after study drug discontinuation

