9.4.6 Prior and Concomitant Therapy

Any medication (including OTC medications) or therapy administered to the subject during the study (starting at the date of informed consent) will be recorded on the Prior and

Concomitant Medication Case Report Form (CRF) or Non-Pharmacological Procedures CRF. The investigator will record on the Adverse Event CRF any AE for which the concomitant medication/therapy was administered. If the concomitant medication/therapy is being administered for a medical condition present at the time of entry into the study, the investigator will record the medical condition on the Medical History and Current Medical Condition CRF.

Other products intended for weight loss including prescription drugs, OTC drugs, and herbal preparations are prohibited as concomitant medications. OTC cold medicines containing dextromethorphan can be used for up to 7 days and study medication is temporarily stopped for that time period and resumed the next day after the OTC cold medicine is stopped. Any of the following serotonergic agents in combination with Belviq XR is prohibited:

a. Serotonergic drugs

- SSRIs
- SNRIs
- TCAs
- bupropion
- triptans
- St. John's Wort
- tryptophan
- MAOIs
- linezolid
- dextromethorphan
- lithium
- tramadol
- antipsychotics or other dopamine antagonists

b. Others

- antiseizure medications including valproic acid, zonisamide, and lamotrigine
- oral steroids (topical or inhaled steroids are acceptable)
- stimulant medications (Ritalin, Concerta, Biphedamine and Dexedrine)
- benzodiazepines

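### The medication definitions in Section 9.7.1.5 leave drugs started before the first dose and still being taken in neither the prior nor the concomitant summary

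*Protocol*

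**What the plan says.** The current protocol deals with this in Section 9.7.1.5, in two definitions. The first reads "Prior medications will be defined as medications that stopped before the first dose of study drug". The second takes concomitant medications to be "medications that started on or after the date of the dosing of study drug and continued up to 30 days afterward". The section tabulates these two classes and no other: the number and percentage of "subjects who took prior and concomitant medications will be summarized for the Safety Analysis Set by treatment group".

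Other sections show that treatment already under way at entry is expected:

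- Section 9.3.2, criterion 10, exempts from the clinically significant disease exclusion "Type 2 diabetes treated with oral anti-diabetic agents (excluding sulfonylurea) or non-insulin injectable antidiabetic agents", and also "obstructive sleep apnea, dyslipidemia, and nonalcoholic fatty liver disease".
- Section 9.3.2, criterion 22, says that subjects with uncontrolled hypertension at Screening "can be rescreened more than 1 month after initiation or adjustment of antihypertensive therapy 1 time".
- Section 9.3.2, criterion 27c, expects users of hormonal contraceptives to have been stable on one product for at least 4 weeks before dosing and to stay on it.
- Section 9.4.6 has all medication recorded on the CRF from the date of consent. It gives a specific instruction for therapy that "is being administered for a medical condition present at the time of entry into the study".

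**The concern.** The two definitions use different tests. *Prior* depends on the stop date and *concomitant* on the start date. A drug that began before the first dose and did not stop fails both. That is how a long-standing antidiabetic or antihypertensive prescription will look in the data.

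Section 9.7.1.1.2 lists as secondary endpoints the changes in HbA1c, fasting glucose, insulin, HOMA-IR, blood pressure and fasting lipids, and the Week 52 proportions with prehypertension or hypertension and with dyslipidemia. A reader judging a difference between arms on any of these will want to know whether background treatment was balanced. The medication tables are where one looks for that, and as defined they would show only what had stopped before dosing and what was newly begun.

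The end of the concomitant window is also unclear. The text refers to the date of dosing without saying whether the first or the last dose is meant.

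**Working it through.** No arithmetic is needed to find the gap. Let D1 be the date of the first dose and classify every possible medication by its start and stop dates.

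| Pattern | Start | Stop | Prior (stop before D1)? | Concomitant (start on or after D1)? | Table |
|---|---|---|---|---|---|
| (a) | before D1 | before D1 | yes | no | prior |
| (b) | before D1 | on or after D1, or ongoing | no | no | none |
| (c) | on or after D1 | any later date, or ongoing | no | yes (subject to the window) | concomitant |

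Pattern (b) is in neither table. The clause about 30 days does not rescue it, because that clause limits how late a medication counts, while pattern (b) fails on its start date.

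**Who falls in pattern (b).**

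- *Antidiabetic drugs.* Criterion 10 admits subjects whose type 2 diabetes is already being treated. That treatment began before D1 and is in pattern (b) if it continues.
- *Antihypertensive drugs.* Criterion 22 requires more than 1 month between starting or adjusting therapy and rescreening, and rescreening precedes D1. The start date is therefore before D1 by construction, and continued therapy is in pattern (b).
- *Hormonal contraceptives.* Under criterion 27c a user has at least 4 weeks on the product before dosing and stays on it. This is again pattern (b).
- *Lipid-lowering drugs.* Criterion 10 permits dyslipidemia, and Section 9.4.6 does not list lipid drugs as prohibited. Their use is an inference; the protocol does not mention them.

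**Whether another section closes the gap.** The baseline characteristics in Section 9.7.1.4 are age, height, BMI, waist circumference, weight, sex and race, with no background therapy. Section 9.7.1.5 does not promise a listing of all medications. Nothing in the current text puts pattern (b) drugs into a by-arm display.

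**The window.** If the 30 days run from the first dose, they cover 30 of 52 × 7 = 364 treatment days, which cannot be intended for a table of on-study medication. If they run from the last dose, they extend past the last scheduled medication check for completers. The medication row of Table 2 is marked at Visits 1 to 11 (Week 52), at unscheduled visits and at early discontinuation, and is blank at the EOS visit in Week 56, which is (56 − 52) × 7 = 28 days later. After Week 52 a completer's medication rests only on the general recording rule in Section 9.4.6.

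**After correction.** If concomitant means taken on or after D1, whether already ongoing or begun later, then (a) is prior, and (b) and (c) are concomitant. Within the window, each medication falls in exactly one class.

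**The case against.** The best case for leaving this alone is that little depends on it. Section 9.4.6 has every medication from consent onward on the CRF, so nothing is lost from the database. The definitions feed a descriptive summary on the Safety Analysis Set; no model, covariate, endpoint or analysis set in Sections 9.7.1.2 and 9.7.1.6 uses them. Sections 9.7.1 and 9.7.4 defer further detail to the SAP, which could sort medications by date correctly. All of that stands and limits the size of the point. It does not make the sentence right: the protocol does not leave the definition open but states one that produces an incomplete table.

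Several stronger readings are tempting and are not supported:

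- *That prohibited drugs begun before dosing would go unnoticed.* Criteria 7 and 8 of Section 9.3.2 restrict weight-loss products and serotonergic drugs before Screening or randomization, and Section 9.4.6 prohibits them on study. Section 9.7.1.2 removes subjects with eligibility violations or major deviations from the per-protocol set. Detection does not rest on this table.
- *That the omitted drugs bias the BMI result.* The protocol does not say that antidiabetic, antihypertensive or lipid drugs alter BMI, and the primary analysis does not use these definitions.
- *That 30 days is wrong because adverse events use 28.* Sections 9.5.4.1 and 9.7.1.8.2 do use 28 days after the last dose, but nothing requires the medication window to match. The defect is the missing anchor.
- *That all antidiabetic and antihypertensive use disappears.* The same drugs begun on study are counted as concomitant.

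**Conclusion.** The point holds as an error in a stated definition. Under Section 9.7.1.5, medications begun before the first dose and still taken appear in neither summary, and the eligibility criteria ensure that such medications are expected. The by-arm tables would understate background antidiabetic and antihypertensive therapy in both arms, and probably lipid-lowering therapy too, though that last is inferred.

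Its size is limited. The loss from the tables is complete for pattern (b), but the protocol does not say how many subjects will be on such therapy, so no count or percentage can be given. What suffers is the interpretation of the glycemic, blood pressure and lipid secondary endpoints. Data capture and the primary BMI analysis are not affected.

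The conclusion assumes that Section 9.7.1.5 is applied as worded. A SAP that classified ongoing drugs as concomitant would repair the tables in practice, but would depart from the protocol's definition in doing so. Because the correction is so small, it should be made.

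**What to change.** Keep the definition of prior medication. Replace the definition of concomitant medication with: any medication taken on or after the first dose of study drug, whether it was started earlier and was ongoing at the first dose or was started on or after it.

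State separately that the post-treatment window runs from the last dose, and give it a length consistent with when medications are collected. As Table 2 stands, that means either ending the window at the last scheduled medication assessment or adding that assessment to the Week 56 visit if a longer window is wanted.

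The main change costs one sentence and needs no new data, because start and stop information is already recorded from consent. Only a window extending beyond Week 52 for completers would call for an extra scheduled check.
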